#### c. Incidental Findings

All subjects will be informed in a timely manner, both verbally and in writing, of any new information, findings or changes to the way the research will be conducted that are of potential relevance for participants and might influence their willingness to continue in this study.

#### d. Data handling and analysis

Only the approved members of the GP surgery will have access to patient identifiable information. Each sample sent for testing will be assigned a study ID to ensure anonymity (pseudonymised). Patient identifiable information will be needed to match questionnaire and medication information with the study samples. This information will be stored on an encrypted, password protected database. Patient identifiers to the study will be held in the same clinical (EmMIS/SystemOne) EHR in the same way information is recorded for the patient population.

Raw genomic data will be generated in a laboratory compliant with GLP and data deleted after a specified time period after transfer for processing by Congenica.

Data at Congenica will be managed, stored and processed according to Congenica's security and data management policies. Congenica is certified to ISO27001:2017 and as such has matured data and information security management processes in place. The company is committed to the confidentiality of personal information and its responsibilities with regard to disclosure of such information. The company has roles of Caldicott Guardian (Chief Scientific Officer) and Senior Information Risk Owner (Quality Assurance and Regulatory Affairs Manager) as these are legal requirements for NHS governance. The Chief Executive Officer is responsible for ensuring that Congenica complies with the pseudonymisation requirements as set out in client contracts. The Quality Assurance and Regulatory Affairs Manager is responsible for ensuring this policy is up to date and complies with current legislation and regulations. All employees, contractors and associates share the responsibility for ensuring that personal identifiable information is handled in accordance with this policy and are trained appropriately to do so. Any changes to policy are communicated to all staff and their acceptance acknowledged in individual training records. Confluence and JIRA systems are used to manage policies, SOPs, work documents etc and perform risk assessment.

Congenica have a quality management system in place (ISO13485:2016) and has Information Governance/NHS Digitial (organisations which have access to NHS patient data and systems must undergo self-assessment to provide assurance that they are practising good data security and that personal information is handled correctly. In addition, Congenica has Cyber Essential certification. Data will have restricted access and only be accessible by authorised individual's that require access to work on the project.

Genomics data is stored in Amazon Web Services, which also holds ISO27001:2013 accreditation. All suppliers to Congenica, including services such as AWS, are reviewed prior to purchasing, following a supplier approval process, where any potential risks to the quality standards in place by Congenica by using the supplier are measured and mitigation put in place. All suppliers are reviewed on an annual basis.

Genomic data for pharmacogenomic reports will be processed by Abomix. Abomix operate under an ISO 13485 quality system but we are not currently accredited by a third party. The software we use for the PGx Interpretation Service is classified as an internal software for producing a service under Finnish legislation (http://www.finlex.fi/data/normit/39643-maarays\_2\_2010\_laiterekis teri\_ilmoitus.pdf) which is under the supervision of Valvira the National Supervisory Authority for Welfare and Health.

Metadata and pseudonymised reports will be stored in a customised OpenApp registry. OpenApp are currently undergoing ISO27001 (Information Security Management) and have been implemented as a patient registry of choice for multiple studies, including European Reference Networks for rare disease. OpenApp follow the anonymisation code of practice as published by the

UK Information Commissioner in 2021.

## 14 Archiving arrangements

Genomics data (pseudonymsed) will be stored in Amazon Web Services, which also holds ISO27001:2013 accreditation. Pseudonymsed metadata collected from the study will also be held on AWS after the end of the study. The sponsor and general practicioners recruiting to the study will have access to this pseudonymsed data.

The agreed archiving period for this trial will be 10 years.

## 15 Statistical design

#### a. Endpoints

## 15.1.1 Primary endpoints

The number of patients with currently actionable variants identified.

- Rate of recommendations for prescription changes
- The prescribing decisions made on receipt of the Pgx data.
- Factors contributing to whether recommendations are or are not converted to medication change within the medication review.

#### 15.1.2 Secondary endpoints

# and type of adverse effects reported by patients pre and post receipt of PGx data # Actionable PGx variants which do not impact on current medication Anxiety measures at baseline, 1 mth, 3 mths, 6 mths and 1 year after consent Patient acceptance of the use of PGx

The time taken to process and receive DNA/PGx results from the time of consent to the project. Fraility index measures at baseline, 1 mth, 3 mths, 6 mths and 1 year after consent Service use review (eg. #hospital admissions, GP appointments and recorded adverse effects at baseline and 1 year)

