## 4 Background

Polypharmacy, the use of multiple medications (3 or more) at the same time is common amongst older individuals and/or in people with multiple co-morbidities. In these populations, medicines are frequently associated with adverse drug reactions (ADRs), falls risk and may have a negative impact on both cognition and quality of life. There are an estimated 237M medication errors per year in the NHS (England), with 66M of these potentially clinically significant.

"Definitely avoidable" adverse drug reactions collectively cost ~£100M annually, contribute to ~1700 deaths/year and are directly responsible for an additional ~700 deaths/year. Evidence demonstrates that over 40% of ADR-related hospital admissions may be preventable.

Pharmacogenomics (PGx), the study of how genes affect an individual's response to drugs, aims to provide information to improve safety and effectiveness of drug treatment. Pharmacogenomic information can be considered actionable if it leads to a change in prescribing decisions, such as alternative medications or dosing. PGx has been shown to be effective for preventing potential side effects of polypharmacy. As a strategy for optimizing medication usage, PGx is becoming an important element of precision medicine with significant potential impact in older people with polypharmacy.

This research study aims to investigate the use of a PGx-led approach to the management of polypharmacy. The aim is to assess outcomes e.g., actionable PGx DNA sequence variants, deprescribing, reduced ADRs and effect on number and length of hospital admissions and General Practice (GP) visits.

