#### 10.2 Questionnaire

Information on patients adverse reactions will be gathered in the form of review of patient records by their GP and questionnaires at multiple timepoints throughout the study; pre-PGx report, 1 month, 3 month, 6 month and 12 month post-medication review (see appendix 1). This will include capture of data on number of GP visits, medication use, hospital admissions, adverse drug reactions

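### Follow-up for anxiety and frailty is timed from consent in the endpoints, while the questionnaires are timed from medication review in the procedures, so nominal follow-up measures can fall before the result or review

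*Protocol*

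**What the plan says.** Section 15.1.2, repeated in the synopsis, times two repeated measures from consent: "Anxiety measures at baseline, 1 mth, 3 mths, 6 mths and 1 year after consent" and "Fraility index measures at baseline, 1 mth, 3 mths, 6 mths and 1 year after consent".

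Section 10.2 is the only place where the protocol schedules questionnaires. It uses the same nominal months but counts them from another event: "pre-PGx report, 1 month, 3 month, 6 month and 12 month post-medication review". It lists adverse drug reactions, GP visits, medication use and hospital admissions as content. It does not name anxiety or frailty, and refers to Appendix 1 for the questionnaire itself, which is a separate file not reproduced in the protocol.

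The adverse-effect endpoint in section 15.1.2 is divided at a third event: the number "and type of adverse effects reported by patients pre and post receipt of PGx data".

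The interval that would link these dates is not given. Part of it is an outcome of the study: "The time taken to process and receive DNA/PGx results from the time of consent to the project". Service use is compared at baseline and 1 year, without saying from which event the year runs.

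**The concern.** Either the same visits carry two clocks, or anxiety and frailty have a second set of visits that no procedure section describes. A site cannot schedule consistently on either reading.

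Consent, return of the report and medication review are different days. Section 10.3 puts saliva shipment, DNA extraction, array genotyping, data transfer, report generation by an outside company and return to the GP between the first and the second. The review comes after that. If the consent clock is followed as written, a measure labelled as follow-up can be taken before the report exists or before anyone has acted on it. For anxiety in particular, such a measure cannot show a response to the result. If some sites follow section 15.1.2 and others section 10.2, the same visit label will mean different things in the two practices.

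The background makes these outcomes matter beyond logistics: "The aim is to assess outcomes e.g., actionable PGx DNA sequence variants, deprescribing, reduced ADRs and effect on number and length of hospital admissions". Section 15 b also expects the data to support the design of a powered study, which needs change scores taken at a known distance from the intervention.

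**Working it through.** There is no stated figure to reproduce, because the protocol gives no lag. The check sets the schedules side by side and shows what follows for a range of assumed lags.

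**Inputs**
- Visit months t = 1, 3, 6, 12 (synopsis, sections 10.2 and 15.1.2).
- Origin: consent (synopsis, 15.1.2) or medication review (10.2).
- L = months from consent to medication review. Not in the protocol; assumed from 0.5 to 4, the same for everyone for simplicity. In practice it will vary between participants.
- Accrual of 500 over 15 months (section 15 b). Latest study end at 20 months (section 9.4). Uniform accrual from month 0 is assumed.

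**Step 1. Position of consent-clock visits relative to review: t − L months**

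| Assumed L | 1-month visit | 3-month visit | 6-month visit | 12-month visit | At or before review |
|---|---|---|---|---|---|
| 0.5 | 0.5 | 2.5 | 5.5 | 11.5 | 0 of 4 |
| 1 | 0 | 2 | 5 | 11 | 1 of 4 |
| 2 | −1 | 1 | 4 | 10 | 1 of 4 |
| 3 | −2 | 0 | 3 | 9 | 2 of 4 |
| 4 | −3 | −1 | 2 | 8 | 2 of 4 |

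A zero is the day of review and a negative value is before it.

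**Step 2. Effect on the change score.** Suppose receiving and acting on the result shifts a score by d, and a share p of participants have had their review by a given consent-clock visit. The mean shift seen at that visit is then p × d, which is smaller than d whenever p is below 1. With L = 2 for everyone, p = 0 at the 1-month visit, so that visit carries no information on the response.

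**Step 3. Adverse effects.** The endpoint divides time at receipt of the PGx data. The pre-report questionnaire sits before that date, but the later ones count from the review. Events between report and review are post by the endpoint's definition, yet precede any change made at the review. The split and the schedule therefore do not share an origin either.

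**Step 4. Cost of moving the clock to review.** Participants who can reach the 12-month visit by month 20 number 500 × (20 − 12 − L)/15.
- Consent clock (L = 0): 500 × 8/15 = 267.
- Review clock with L = 2: 500 × 6/15 = 200.

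Section 9.4 also allows the study to end when the last participant's sample arrives. An end at about month 15 would lower these to 500 × 3/15 = 100 and 500 × 1/15 = 33.

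**The case against.** The strongest reply is that section 10.2 never names anxiety or frailty, so the two schedules might concern different instruments. The questionnaire file, flow chart and patient journey are not available here and might settle it. A consent clock for anxiety could even be deliberate, to capture worry while waiting for a result. This narrows the point but does not remove it. The text gives no other procedure for anxiety or frailty, uses identical months in both places, and states no reason for two clocks.

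It is also fair to say that the lag is unknown and may be short. At half a month the shift hardly matters, and even at 3 months the 6- and 12-month measures follow the review. A reader might infer that pre/post change is therefore uninterpretable. The protocol does not support that: later visits remain usable, and the ambiguity is one of timing.

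A reader might also infer that one questionnaire before and four after will inflate adverse-effect counts fourfold. With equal recall windows and no true change, a summed post count would indeed be 4/1 = 4 times the pre count. But nothing in the protocol says the four are summed, and one baseline with several follow-ups is an ordinary schedule. The recall windows may be in the questionnaire file. GP record review (section 10.2) and the baseline versus 1-year service-use comparison do not carry the imbalance, and repeated scores such as anxiety and frailty are not inflated by it. Compared per time point with equal windows, the expected ratio is 1.

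Finally, a reader might fault the lack of a comparator. The study is declared a case series and feasibility study. The protocol does not say that participants without a recommended change are followed on the same schedule, so no ready-made comparison group can be assumed.

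**Conclusion.** The time origins conflict: consent for anxiety and frailty, medication review for the questionnaires, and receipt of the PGx data for the adverse-effect split. Because the protocol treats the time from consent to result as something to be measured, the conflict cannot be dismissed as harmless.

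Its size depends wholly on the lag: negligible at half a month, one of four follow-ups at or before review at 1 to 2 months, and two of four at 3 to 4 months. These lags are assumptions, and a single lag for all participants is a simplification. The consequence is diluted change in anxiety and frailty at the early visits, and a 12-month measure taken short of 12 months after review.

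The primary endpoints do not depend on this clock. The point should be fixed, preferably before follow-up starts, since a visit taken at the wrong time cannot be retaken.

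**What to change.** 1. Reconcile the synopsis, section 10.2 and section 15.1.2. Anchor anxiety, frailty and adverse-effect follow-up to one event, either the medication review or return of the PGx report, and take baseline before the report is returned. State the origin of the 1-year service-use comparison as well.
2. Record the dates of consent, report return and medication review for each participant in the registry, so that every measure can be placed relative to all three.
3. State that adverse effects will be compared per time point, or per person-month over matched windows, and not as a pooled post count.

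The direct cost is amendment wording and a change to the registry's visit scheduling. The real downside is that every visit moves later by the turnaround time. Under the assumptions in the check, about 200 of 500 participants instead of 267 would reach the 12-month measure by month 20 if the lag is 2 months. Section 9.4 therefore has to be reconciled with the 12-month follow-up in the same amendment, or the shortfall accepted and stated.

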#### b. Sample size calculation

We aim to recruit 500 families over the course of 15 months at two sites. This is a realistic number of eligible cases based on inclusion criteria. By the end of this time we will have enough proof-of-principle data to enable design and execution of an appropriately powered clinical study.

## c. Statistical analysis plan

Statistical analysis is not required for this study.

## 16 Ethics and Research Governance requirements

Before the site can enrol patients into the study, the Principal Investigator must ensure that written permission to proceed has been granted in compliance with the protocol as agreed by the Sponsor and which was accepted by the Research Ethics Committee (REC).

It is the responsibility of the CI to ensure that all subsequent amendments gain the necessary approval.

Within 90 days after the end of the study, the CI and Sponsor will ensure that the REC is notified that the study has finished. If the study is terminated prematurely, those reports will be made within 15 days after the end of the study

The CI will supply an End of Study report of the clinical trial to the REC within one year after the end of the trial.

#### a. Direct access to source data

The Investigator(s)/institution(s) will permit trial-related monitoring, audits, REC review, and regulatory inspection(s), providing direct access to source data/documents. Trial participants are informed of this during the informed consent discussion. Participants will consent to provide access to their medical notes.

#### 17 Finance

The trial is funded by Innovate UK and Congenica Ltd, a leading provider of clinical decision support software andservices who have developed the gold-standard platform, Congenica, for analysis, interpretation and generation of clinically actionable reports on patient derived genomic data.

## 18 Insurance and indemnity

Congenica is the sponsor for this study and will provide indemnity to meet the potential legal liability of the sponsor harm to participants arising from the management of the research and design of the research.

NHS indemnity scheme will apply to the NHS investigators in the design of research and conduct of research. NHS bodies are liable for clinical negligence and other negligent harm to individuals coveredby their duty of care. NHS Institutions employing researchers are liable for negligent harm caused by the design of studies they initiate.

## 19 Development policy

The sponsor, participating sites and all investigators involved in the study shall treat all information and data related to the study as confidential and with the proper respect for the privacy of each participant. The parties shall equally warrant to not disclose such information to third parties or disclose such publicly, but shall use such information solely for the purpose of this study. All data shall be coded or de-identified prior to transfer of such data to sponsor.

The participating site and their proper investigators warrant that they shall not perform the study without having obtained the proper, written informed consent from each participant, in accordance with applicable legislation and as approved by the appropriate ethics committee/review board.

## 20 Publication policy

Publication: "Any activity that discloses, outside of the circle of study investigators, any final or interim data or results of the study, or any details of the study methodology that have not been made public by the Sponsor including, for example, presentations at symposia, national or regional professional meetings, publications in journals, theses or dissertations."

All scientific contributors to the study have a responsibility to ensure that results of scientific interest arising from study are appropriately published and disseminated. The Sponsor has a firm commitment to publish the results of the study in a transparent and unbiased manner without consideration to commercial objectives.

To maximise the impact and scientific validity of the study, data shall be consolidated over the duration of the study, reviewed internally among all investigators and not be submitted for publication prematurely.

## a. Before the official completion of the Study

All publications during this period are subject to permission by the Sponsor. If an investigator wishes to publish a sub-set of data without permission of the Sponsor during this period, the steering committee shall have the final say.

#### b. Up to 180 days after the official completion of the Study

During this period the Chief Investigator shall liaise with all investigators and strive to consolidate data and results, then submit a manuscript for peer review with a view to publication in a reputable academic journal or similar outlet as the Main Publication.

- i. The Chief Investigator shall be senior and corresponding author of the Main Publication.
- Insofar as is compatible with the policies of the publication outlet and good academic practice, the other Investigators shall be listed in alphabetic order.
- iii. Providers of analytical or technical services shall be acknowledged, but will be listed as co-authors only if their services were provided in a non-routine manner as part of scientific collaboration.
- iv. Members of the Steering Group shall be acknowledged as co-authors only if they also contributed in other capacities.
- v. If there are disagreements about the substance, content, style, conclusions, or author list of the Main Publication, the Chief Investigator shall ask the Steering Group to arbitrate.

## c. Beyond 180 days after the official completion of the Trial

After the Main Publication or after 180 days from study end date, any Investigator or groupof investigators may prepare further publications. In order to ensure that the Sponsor will be able to make comments and suggestions where pertinent, material for public dissemination will be

submitted to the Sponsor for review at least sixty (60) days prior to submission for publication, public dissemination, or review by a publication committee. Sponsor's reasonable comments shall be reflected. All publications related to the study shall credit the Chief and Co-Investigators as co-authors where this would be in accordance with normal academic practice and shall acknowledge the Sponsor and the Funders.

## 21 Statement of Compliance

The study will be conducted in compliance with the protocol, Sponsor's Standard Operating Procedures (SOPs), GCP and the applicable regulatory requirement(s).

The study conduct shall comply with all relevant laws of the EU if directly applicable or of direct effect and all relevant laws and statutes of the country in which the study site is located, including but not limited to the Human Rights Act 1998, the Data Protection Act 1998, the Human Medicines Regulations 2012, ICH GCP, the World Medical Association Declaration of Helsinki entitled 'Ethical Principles for Medical Research Involving Human Subjects' (2008 Version), the NHS Research Governance Framework for Health and Social Care (Version 2, April 2005).

This study will be conducted in compliance with the protocol approved by the REC and according to GCP standards. No deviation from the protocol will be implemented without the prior review and approval of the Sponsor and REC except where it may be necessary to eliminate an immediate hazard to a research subject. In such case, the deviation will be reported to the Sponsor and REC as soon as possible.

## 22 List of Protocol appendices

**Appendix 1** Questionnaire

**Appendix 2** Flow chart

[figure not shown]
**Appendix 3** Patient journey

# Appendix 1

See file 'HAPPY protocol v1.3 Appendix 3.xlsx'

# Appendix 2

Study flow chart

